7 STUDY TREATMENT(S)

7.1 Description of investigational medicinal product

Levetiracetam dry syrup 50% (white to off-white granules) for oral administration will be used in this study. Levetiracetam injection (100mg/mL) will also be used.

7.2 Treatments to be administered

Each subject will be weighed in kg and will receive 2 equal oral doses of LEV dry syrup 50% dissolved in water; 1 in the morning and 1 in the evening. The weight obtained at every visit will be used to calculate the dose of study medication (mg per kg) for the entire study.

If the subject cannot take LEV dry syrup under a fasting state during the First Period, LEV 100mg/mL concentrate for solution for infusion (clear, colorless, sterile solution) can be used for a maximum of 4.5 consecutive days at each dose at the Investigator's discretion. Levetiracetam injection is infused intravenously over 15 minutes per dose.

The weight and amount of individual dose will be recorded in the CRF and in the drug accountability log for the site. Medication will be allocated by the IVRS.

First Period

Once the subject has fulfilled the eligibility criteria, the subject will enter the Evaluation Period.

Study medication should be given as 2 equally divided doses administered twice daily. The first intake of newly dispensed study medication should occur at Visit 3. Subjects should take IMP according to instructions provided by the Investigator.

[figure not shown]
Subjects aged 1 month to < 6 months will be started on LEV 14mg/kg/day at Visit 3 (Week 0). The dose may be increased by LEV 14mg/kg/day for subjects aged 1 month to < 6 months at 2-week intervals to a maximum dose of LEV 42mg/kg/day. Subjects aged 6 months to < 4 years will be started on LEV 20mg/kg/day at Visit 3 (Week 0). The dose may be increased by LEV 20mg/kg/day at 2-week intervals to a maximum dose of 60mg/kg/day.

At the end of the Evaluation Period, subjects will enter into the Second Period. Subjects who do not enter the Second Period will enter the Down-Titration Period, followed by the Safety Follow-Up Period.

The Down-Titration Period (up to 4 weeks) will consist of the following:

- The dose will be decreased by 14mg/kg/day for subjects aged 1 month to <6 months or by 20mg/kg/day for subjects aged 6 months to <4 years at 2-week intervals to 0mg/kg/day.

Figure 7-1: Schematic for Down-Titration and Safety Follow-Up Periods

*: Safety Follow-Up (SFU) is 2 weeks after final dose of study drug.

EDV=Early Discontinuation Visit; SFU=Safety Follow-Up; V=Visit

Note: The value in parentheses for dose is for subjects 1 month to <6 months of age.

The down-titration procedure needs to be applied in case of early discontinuation.

Second Period

For continuing subjects, if a dose adjustment becomes necessary, the investigators will increase or decrease the dose by at least a 2-week interval. One increase or decrease in the dose should not exceed LEV 14mg/kg/day for subjects aged 1 month to <6 months or LEV 20mg/kg/day for subjects aged 6 months to <4 years for the 2-week interval. The dosage can be adjusted to LEV 14, 28 and 42mg/kg/day LEV for subjects aged 1 month to <6 months or LEV 20, 40 and 60mg/kg/day for subjects aged 6 months to <4 years at the Investigator's discretion for the benefit/risk for individual subjects.

Subjects who withdraw or complete the Second Period will enter the Down-Titration Period, followed by the Safety Follow-Up Period.

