1 SUMMARY

EP0100 is an open-label, single-arm, multicenter study with levetiracetam (LEV) as monotherapy or adjunctive treatment to evaluate the efficacy and safety of LEV in Japanese subjects aged 1 month to <4 years with partial seizures. The study will consist of 2 periods. The First Period is designed to confirm efficacy of LEV, and the Second Period is designed to evaluate the long-term efficacy and safety of LEV. Subjects with uncontrolled partial seizures will be enrolled into the Selection Period of the First Period.

Seizure counts during the 2 weeks prior to Visit 1 will be used as a Retrospective Baseline. All eligible subjects will enter a 6-week Evaluation Period. Subjects aged 1 month to <6 months will be started on LEV 14mg/kg/day at Visit 3 (Week 0). The dose may be increased by LEV 14mg/kg/day for subjects aged 1 month to <6 months at 2-week intervals to a maximum dose of 42mg/kg/day. Subjects aged 6 months to <4 years will be started on LEV 20mg/kg/day at Visit 3 (Week 0). The dose may be increased by LEV 20mg/kg/day at 2-week intervals to a maximum dose of 60mg/kg/day.

At Visit 6 (Week 6), subjects may enter the Second Period or enter the Down-Titration Period followed by a Safety Follow-Up Period. Subjects who do not enter the Second Period will be down-titrated. The dose will be decreased by LEV 14mg/kg/day for subjects aged 1 month to <6 months or by LEV 20mg/kg/day for subjects aged 6 months to <4 years at 2-week intervals to 0mg/kg/day. Subjects who withdraw from the study at the minimum age-related dose do not need to down-titrate. In order to provide LEV to subjects who completed the First Period, the Second Period will be conducted until approval or the program is discontinued.

All subjects who do not enter the Second Period will enter the Safety Follow-Up Period, regardless of whether they down-titrate LEV.

After approval in Japan for the indication of LEV as monotherapy or adjunctive treatment in patients aged 1 month to <4 years with partial seizures, this clinical study (Phase 3) will be continued as a postmarketing clinical study (Phase 4). All subjects who are still in the study as of the date of approval will be considered to have completed the study. After the date of approval, subjects should visit the investigational site as soon as possible to complete the study by switching to commercial LEV or discontinuing LEV after the assessments specified in Section 8.5 "Early Discontinuation Visit" in the protocol.

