5.1.3 Second Period

Subjects who complete the First Period will have a visit every 4 weeks \pm 7 days relative to Visit 3 for the first 6 months of administration and then every 12 weeks \pm 14 days thereafter. Subjects will continue to receive LEV 14 to 42mg/kg/day in subjects aged 1 month to <6 months or LEV 20 to 60mg/kg/day for subjects aged \geq 6 months <4 years at the discretion of the Investigator.

When subjects aged <6 months at the time of study enrollment reach 6 months of age, they can take a maximum of LEV 60mg/kg/day.

A final visit will be required 2 weeks \pm 7 days after the final dose of LEV, or sooner if the subject will continue LEV (prescribed by the primary care provider as commercial LEV) after study completion.

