3.2.1.2 End Date of the First/Second Period

A subject is regarded to have started/ended a period as described below. For this, the start dates and end dates of study periods for each subject are defined in the following sections.

3.2.1.2.1 Subjects enrolled prior to Protocol Amendment 3 who are not 48h video-EEG Failures and subjects enrolled according to Protocol Amendment 3

3.2.1.2.1.1 First period

Selection Period:

- Start: Day of Visit 1
- End:
 - Subject does not discontinue from study: 1 day before Visit 3, or
 - Subject discontinues from study: “Date of last contact with Subject” on “Study Termination, Screen Failure Packet” CRF.

Evaluation Period (only if subject does not discontinue before or at Visit 3):

- Start: Day of Visit 3
- End:
 - First of:
 - Day of Visit 6, or
 - Day of first Early Discontinuation Visit.

For subjects who do not enter the Second Period:

Down-Titration Period (only when subject is not on minimum dose):

- Start: 1 day after Day of End of Evaluation Period
- End: Day of Last Early Discontinuation Visit; if Day of Last Early Discontinuation Visit is missing, the date of last dose of study medication will be used

Followed by

Safety Follow-Up Period (safety follow-up visit will take place when subject is 2 weeks off study drug, ie, on 0mg/kg dose):

- Start: 1 day after Day of End of Down-Titration Period or 1 day after Day of End of Evaluation Period
- End: Day of Safety Follow-Up Visit

3.2.1.2.1.2 Second Period

Maintenance period:

- Start: 1 day after Day of Visit 6
- End: First of:
 - Day of first Early Discontinuation Visit, or
 - Day of End of Study*

- * Day of End of Study as determined by sponsor, connected to market approval or completion of development of LEV in subjects 1 month to <4 years

Down-Titration Period (only when subject is not on minimum dose):

- Start: 1 day after Day of End of Maintenance Period
- End: Day of Last Early Discontinuation Visit; if Day of Last Early Discontinuation Visit is missing, the date of last dose of study medication will be used

Followed by

Safety Follow-Up Period (safety follow-up visit will take place when subject is 2 weeks off study drug, ie, on 0mg/kg dose):

- Start: 1 day after Day of Down-Titration Period or 1 day after Day of End of Maintenance Period
- End: Day of Safety Follow-Up Visit

For subjects who did not discontinue from Maintenance Period:

- The end date will be captured on “study termination” CRF.

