- No down-titration and Safety Follow-Up will be performed for these subjects.

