10.2.1.2 Assignment of AEs to Periods/Onset of AEs

An AE is assigned to that study period the subject is in during onset of the AE. For the definitions of study periods see [Section 2.3.1](#).

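### Protocol 7.2 and SAP 3.2.1.2 give opposite rules for children who complete the Second Period, and the SAP defines no post-Maintenance period for completers who stop LEV

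*Protocol*

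**What the plan says.** Four places describe how treatment ends for a child who stays in the study to the end of the Second Period.

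- **Protocol 7.2**, Second Period: "Subjects who withdraw or complete the Second Period will enter the Down-Titration Period, followed by the Safety Follow-Up Period". Continuing on commercial LEV is not mentioned.
- **SAP 3.2.1.2**, once for the main cohort and again for 48h video-EEG failures: "For subjects who did not discontinue from Maintenance Period", the end date comes from the study termination form and "No down-titration and Safety Follow-Up will be performed for these subjects".
- **Protocol 1**: "All subjects who are still in the study as of the date of approval will be considered to have completed the study". These children then attend the site to "complete the study by switching to commercial LEV or discontinuing LEV after the assessments specified in Section 8.5", the Early Discontinuation Visit. Safety Follow-Up is not named.
- **Protocol 5.1.3**, repeated in SAP 2.3: a final visit 2 weeks ± 7 days after the last dose, "or sooner if the subject will continue LEV (prescribed by the primary care provider as commercial LEV) after study completion".

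For adverse events, SAP 10.2.1.2 states: "An AE is assigned to that study period the subject is in during onset of the AE". SAP 3.9 records no departure from the protocol-defined analyses.

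**The concern.** Protocol 7.2 and the SAP give opposite answers to whether a completer has a Down-Titration Period and a Safety Follow-Up Period. The weeks in which an antiepileptic drug is reduced and stopped are those in which seizure worsening or other withdrawal events would be looked for. If the SAP recognises no period for that time in completers, an event there has no defined place when events are assigned by period. By-period laboratory and vital-sign percentages (SAP 10.3.1, 10.4.1.1) have the same difficulty, because their denominators are the subjects who entered the period.

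The protocol does not settle the matter by itself. Sections 1 and 5.1.3 allow for a child who moves to commercial LEV, and 7.2 does not.

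**Working it through.** No power or error-rate calculation is involved. The check compares the rules, then counts the weeks, then traces an adverse event.

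**1. The rules side by side**

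| Source | Completer who stops LEV | Completer who continues on commercial LEV |
|---|---|---|
| Protocol 7.2 | Down-Titration, then Safety Follow-Up | Same; no exception stated |
| SAP 3.2.1.2 | Neither | Neither |
| Protocol 1 (approval only) | Section 8.5 assessments, then stop; Safety Follow-Up not named | Section 8.5 assessments, then switch |
| Protocol 5.1.3, SAP 2.3 | Final visit 2 weeks ± 7 days after last dose | Final visit may be sooner |

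Rows 1 and 2 contradict each other in both columns. Row 3 covers approval only. Maintenance can also end because the program is discontinued (Protocol 5.1.4), and then rows 1, 2 and 4 remain.

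**2. Does version timing explain it?** The SAP is based on Protocol Amendment 3 (SAP 2). The amendment log for Amendment 3 (Protocol 17.6, Change #19) carries the same 7.2 sentence, so timing does not explain rows 1 and 2. It may explain part of row 3, because the completion paragraph in Section 1 came with Amendment 4 (Protocol 17.7).

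**3. Weeks in dispute for a completer who stops LEV**

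Inputs: top doses of 60 and 42 mg/kg/day, steps of 20 and 14 mg/kg/day, 2 weeks per step (Protocol 7.2), and follow-up of 2 weeks (Protocol 5.1.4).

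- Dose levels per age band: 60/20 = 3 and 42/14 = 3.
- Down-titration time = number of lower non-zero levels × 2 weeks.
- From the top level: 2 × 2 = 4 weeks. This reproduces the protocol's stated maximum and matches the W0, W2 and W4 visits in Table 5-3.
- From the middle level: 1 × 2 = 2 weeks. From the lowest: 0 × 2 = 0 weeks.
- Adding 2 weeks of follow-up: 4 + 2 = 6, 2 + 2 = 4 and 0 + 2 = 2 weeks.

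Under Protocol 7.2 the post-Maintenance time is therefore 2 to 6 weeks. Under the SAP sentence it is 0. These are nominal lengths, before the ± 7-day visit window.

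**4. Tracing an adverse event in that time**

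- SAP 10.2.1 defines a treatment-emergent event by onset or worsening on or after first dose, with no end date. The event qualifies.
- SAP 10.2.1.2 assigns it to the period the child is in at onset. SAP 2.3.1 lists Down-Titration and Safety Follow-Up within the Second Period, but SAP 3.2.1.2 removes both for completers and ends Maintenance at the first Early Discontinuation Visit or the end of study. No period is left.
- SAP 10.2.2 tabulates events for the First Period and for the combined periods on the Safety Sets. It does not say how an event without a period is handled.

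**The case against.** The strongest reply is that this is a wording conflict with little effect on the data. Much of that stands.

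- *Events would not be counted.* A reader might infer that withdrawal-phase events in completers leave the combined tables. The documents do not support that. The definition of a treatment-emergent event is open-ended, the combined tables run on the Safety Sets, and no text excludes an event that lacks a period. What is missing is the assignment.
- *Events would not be observed.* A reader might infer this too. Sites work from the protocol. Section 11.1.1.1 requires reporting of all adverse events, including in protocol-required posttreatment periods. Section 11.1.3 provides for follow-up of events still ongoing, and 5.1.3 sets a visit after the last dose. A SAP derivation rule does not stop collection. This support is not complete: Section 1 does not name Safety Follow-Up, and the post-study reporting window for serious events in 11.1.2.3 is an unfilled placeholder.
- *Section 1 is a wholly separate rule.* It need not be. The Section 8.5 visits are the W0/W2/W4 series in Table 5-3, which carries the dose-reduction footnote. The rationale for Amendment 4 also distinguishes switching to commercial LEV from stopping after dose reduction. For a child who stops, Section 1 can be read as including down-titration.
- *The protocol takes LEV away from a child who is switching.* That follows only if 7.2 is read alone. Sections 1 and 5.1.3 both provide for continuing on commercial LEV, so 7.2 has a gap in its wording.
- *The SAP definitions could already fit.* For the main cohort, the Second Period Down-Titration definition is limited to subjects not on the minimum dose, not to those who discontinue. A completer with Early Discontinuation Visits could fit it. The sentence that follows, however, says neither period will be performed, so the SAP conflicts with itself as well.

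None of this reconciles 7.2 with the SAP.

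**Conclusion.** The contradiction is real, is in current text, and is not explained by document versions. For a completer who stops LEV, a nominal 2 to 6 weeks after Maintenance has no analysis period under the SAP, and the period assignment of adverse events in that time is undefined. For a completer who switches to commercial LEV there is no drug-withdrawal phase to observe. The conflict between 7.2 and the other passages still applies to that child.

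The number of completers who stop LEV is not given. The planned 38 + 10 = 48 subjects are enrolment, and a reader should not take that as the number affected. The week count assumes that dose is reduced one level at a time as the protocol describes.

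The primary endpoint at Week 6, the sample size, the testing hierarchy and the First Period efficacy results are untouched. This is a consistency error that should be fixed, but the trial's main conclusion does not depend on it.

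**What to change.** - **Protocol and SAP together.** Reconcile Protocol 1, 5.1.3 and 7.2 with SAP 2.3 and 3.2.1.2 (both cohorts), so that they give one account for completers who stop LEV and one for completers who continue on commercial LEV. Which clinical rule is right is for the sponsor and investigators; this review takes no view.
- **SAP 3.2.1.2.** Derive the Down-Titration and Safety Follow-Up Periods from actual study-drug dosing and visits, regardless of completion status, and amend the two blanket sentences to match. A child with no study-drug reduction and no follow-up visit then simply has neither period, so the derivation works whichever clinical rule is adopted.
- **SAP 10.2.1.2 and 10.2.2.** State that adverse events with onset in that time are assigned to those periods and included in the combined First and Second Period tables.

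The cost is a clarifying protocol amendment or memo and a few lines in the SAP, before database lock. Table 5-3 already contains the visits, so the SAP change needs no new procedures.

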7.3 Packaging

A 100g-volume of LEV dry syrup 50% will be filled in a 250mL bottle. Each bottle will be packaged individually. The needed number of the bottles will be dispensed to each study site.

The research pharmacist at the study site(s) will fill out each sachet with the prescribed amount of LEV dry syrup 50%.

Levetiracetam injection (100mg/mL) will be packaged in 5mL glass vials (500mg/5mL). A dose of the drug (500mg to 1500 mg) must be diluted in 100mL of saline, lactate Ringer's solution, or 5% glucose solution. Consideration should be given to reducing the dilution volume for use in children by referring to the dilute concentration for adult use. The drug should be used immediately after dilution.

7.4 Labeling

Clinical drug supplies will be labeled in accordance with the current International Council for Harmonisation (ICH) guidelines on Good Clinical Practice (GCP) and Good Manufacturing Practice and will include any locally required statements. If necessary, labels will be translated into the local language.

7.5 Handling and storage requirements

The investigator (or designee) is responsible for the safe and proper storage of IMP at the site. Investigational medicinal product stored by the investigator is to be kept in a secured area with limited access according to the storage conditions mentioned on the label.

Appropriate storage conditions must be ensured either by controlling the temperature (eg, room, refrigeration unit) or by completion of a temperature log in accordance with local requirements on a regular basis (eg, once a week), showing actual and minimum/maximum temperatures reached over the time interval.

In case an out-of-range temperature is noted, it must be immediately reported as per instructions contained in the IMP Handling Manual.

The investigator (or designee) will instruct the subject to store the IMP following the instructions on the label.

7.6 Drug accountability

A Drug Accountability form will be used to record IMP dispensing and return information on a by-subject basis and will serve as source documentation during the course of the study. Details of any IMP lost, damaged (due to breakage or wastage), not used, partially used, disposed of at the study site, or returned to the sponsor or designee must also be recorded on the appropriate forms. All supplies and pharmacy documentation must be made available throughout the study for UCB (or designee) to review.

The investigator (or designee) is responsible for retaining all used, unused, and partially used containers of IMP until returned or destroyed.

The investigator may assign some of the investigator's duties for drug accountability at the study site to an appropriate pharmacist/designee.

The investigator must ensure that the IMP is used only in accordance with the protocol.

7.7 Procedures for monitoring subject compliance

At each visit after IMP is dispensed, subjects must return all unused IMP and empty IMP containers. Drug accountability must be done in the subject's presence in order to obtain

explanations regarding discrepancies in compliance with the dosing regimen. Drug accountability must be recorded on the Drug Accountability form.

If a subject is found to be persistently noncompliant (<80% or >120% compliant with the dosage schedule), the sponsor, in conjunction with the investigator, will make a decision as to whether the subject should be withdrawn from the study.

7.8 Concomitant medications/treatments

An accurate record of treatments other than the IMP must be kept in the clinic chart (source documentation) and the Case Report form (CRF). This record should include the name of the medication, the dose, the date(s) of administration, and the indication for use.

7.8.1 Permitted concomitant treatments (medications and therapies)

First Period

Subjects on adjunctive therapy must be on a stable regimen of 1 or a maximum of 2 other AEDs for the Selection and Evaluation Periods (Appendix 3 [Section 17.3]). No new AEDs may be added or current AEDs discontinued for at least 2 weeks prior to Visit 1. Minor adjustments to the dose of current AEDs are allowed prior to Visit 1 only.

Subjects on adjunctive therapy who have VNS that have been implanted for at least 6 months prior to Visit 1 are allowed as long as the settings have been stable for at least 2 months prior to Visit 1. Activated VNS must be counted as 1 of the 2 AEDs.

The use of intermittent benzodiazepines, phenobarbital, and phenytoins is allowed as long as the frequency is not greater than 1 single administration per week for at least 2 weeks prior to Visit 1 and during the First Period. If benzodiazepines are used more than once a week, they must be considered as 1 of the AEDs.

Second Period

The Investigator (or designee) will be allowed to change the type, dosage and administration, or discontinue/resume concomitant AEDs to optimize tolerability and seizure reduction for each subject after 3 months of the start of the Second Period. Changes in concomitant AED(s) will be allowed only if the dose of LEV has been stable for the previous 2 weeks; LEV dose must remain stable during changes to concomitant AED(s). Subjects may take no more than 3 concomitant AEDs except when temporary (≤ 12 weeks) use of an additional AED is required to switch to a new AED (ie, taper from old AED during titration of new AED). New AED(s) may be added only when the subject has not optimally or adequately responded to a maximum tolerated dose of LEV. The concomitant AED(s) can be carefully tapered or discontinued at the discretion of the investigator. Monotherapy with LEV is permitted. Increasing the dose of LEV and/or concomitant AED(s), as well as addition of a new AED should be done at a visit (scheduled or unscheduled). There are no restrictions for concomitant AED(s) during the Down-Titration Period, considering subject safety.

The use of intermittent benzodiazepines, phenobarbital, and phenytoins is allowed as long as the frequency is not greater than 1 single administration per week during the Second Period. If benzodiazepines are used more than once a week, they must be considered as 1 of the AEDs.

